3. UDS
4. Pregnancy test (1 or 2, depending on appointment schedules)
5. HIV Dementia Scale (HDS)
6. CES-D depression scale
7. MRI questionnaire

E5 Baseline Visit(s) (can be performed same day as screening visit)

1. Neuromedical exam
2. History & physical
3. Vital signs (BP, HR, height, weight, waist circumference)
4. Assessments, questionnaires, & other evaluations:
NEUROPSYCHOLOGICAL ASSESSMENTS: 1. BVMTR (Bender Visual Motor Gestalt Test -- evaluates visual-perceptual and visual-motor functioning, yielding possible signs of brain dysfunction, emotional problems, and developmental maturity) 2. Hopkins Verbal Learning Test (HVLT -- measure of verbal episodic memory) 3. Trailmaking Parts A and B (measure attention, visual searching, mental processing speed, and the ability to mentally control simultaneous stimulus patterns) 4. Digit-Symbol Substitution Task (measures brain damage, dementia, age and depression) 5. Grooved Pegboard dominant and non-dominant hand (Measures performance speed in a fine motor task. By examining both sides of the body, inferences may be drawn regarding possible lateral brain damage.) 6. Letter-Number Sequencing (tests working memory and attention) 7. Wide Range Achievement Test (3 or 4) (Provides level of performance in reading, spelling, and written arithmetic. The reading and spelling tests are often used in estimating premorbid intellectual functioning.) 8. Timed Gait (standardized procedure assessing motor dysfunction of lower extremities and gait abnormalities associated with AIDS dementia complex) 9. Finger Tapping (measures motor speed) 10. FAS (measures executive cognitive dysfunction) 11. Category Fluency (animals) (tests executive functions and language, as well as semantic memory) 12. Action Fluency (examines verbally mediated executive functions, especially frontal system damage) 13. Stroop Interference Test (tests switching, cognitive flexibility and inhibition) 14. WAIS-III Symbol Search (tests perceptual organization and processing speed) 15. Iowa Gambling Task (computer exercise) (assessment of risk-taking) 16. Medication Management Task (listed as perf meas 1-5 on attachments) 17. Boston Naming Test (measures ability to retrieve words/language disturbance) 18. Digit Span (tests visuospatial and attention domains) 19. Line Orientation (tests visuospatial and attention domains) 20. Rey-Osterrieth Complex Figure Test [Rey-O] (assesses visuospatial abilities, memory, attention, planning, and working memory) 21. Wisconsin Cart Sorting Task [WCST -- computerized] (assesses executive functioning planning use of feedback and shifting) 22. Paced Auditory Serial Addition Task [PASAT] (assessment of speed of information processing) 23. Montreal Cognitive Assessment [MOCA] (screening assessment for mild cognitive impairment) 24. Virtual Week (computerized prospective and retrospective memory assessment)

QUESTIONNAIRES: 25. Lawton & Brody ADL scale (assessment of ability to independently perform activities of daily living) 26. SES questions (looks at subjects' socioeconomic status, as well as previous early life trauma they may have experienced) 27. Risk Assessment Battery (assessment of risk-taking) 28. Beck Depression Inventory (records symptoms of depression subjects have had in the past 2 weeks) 29. KMSK (Kreek-McHugh-Schluger-Kellogg scale -- designed to quantify self-exposure to opiates, cocaine, alcohol, tobacco and/or marijuana) 30. Fagerstrom smoking questions (corrected version) (scale of nicotine dependence) 31. Locator Form (basic contact information, physicians' names, etc.; zip code will be used not only to contact participants, but also to determine median

income for the area in which they live for data analyses) 32. Pittsburgh Sleep Quality Index (assesses sleep quality and disturbances over a 1-month interval) 33. ADL questionnaire (questionnaire of ability to perform activities of daily living) 34. Prospective and Retrospective Memory Questionnaire (PRMQ). 35. International Physical Activity Questionnaire (IPAQ) 36. Substance Use Social Disruption Questions (assessing social disruption from drugs and/or alcohol)

ADDITIONAL ASSESSMENTS: 1. Fried Frailty Assessment 2. Calculation of the VACS index (captures both HIV and aging hallmarks to predict comorbidity and mortality) 3. Patient Centered Assessment and Counseling for Exercise (PACE) (assesses attitudes about exercise, barriers/facilitators to adherence to EXS, exercise enjoyment, self-efficacy and social support); 4. Charlson Comorbidity Index

5. Cardiorespiratory capacity testing (including stationary bicycle workout (VO2 test), DXA & 6 minute walk test). An intravenous line may be placed in the participant's arm. This line may be kept in place for several hours during the cardiovascular evaluation for safety monitoring.
6. Attachment of actigraph at end of visit. Participants will wear the actigraph for approximately 1-2 weeks before and 1-2 weeks after the intervention. They may also be asked to wear it for some duration during the intervention, anywhere from approximately 1 week to the entire intervention.
7. Randomization in a 2:1 ratio to either the Exercise intervention (N=100) or the Social Interaction/Stretching intervention (N=50)
8. Collection of fasting labs (such as but not limited to CMP, sCRP, CBC w/diff, HbA1C, leptin, D-Dimer, YSI, Insulin/IGF-1/C-peptide/Glucagon, plasma BDNF, plasma VEGF, Adiponectin, IL-6, HOMA-IR/fasting glucose & insulin, glycosylated hemoglobin, plasma IGF-1, soluble CD163, plasma neopterin, galectin 9, etc.) and APOE test (APOE will only be done at baseline, not at follow up). CD4 and VL may also be collected if not available through medical records, and approximately 32 mL of blood will also be taken and banked for future use as documented in the Informed Consent.
9. 3T MRI lasting approximately 1 hour
10. Stool sample and dietary survey.
11. Scheduling of dates/times to attend intervention.

E6 Intervention approximately 3x per week for 26 weeks

1. Subject will be able to make up visits, if missed (i.e. If subject comes in 2x during 1 week, they can come 4x the next week for an average of 3x per week).

E7 1 month stool sample and dietary survey

1. Participants will also be given a stool collection kit and asked to bring samples in at baseline, 1 month, mid-point (approx. 3 months), and final follow-up (approx. 6 months). They will also be asked to complete a dietary survey such as the ASA24 or 24 hour food log each time a stool sample is provided.

E8 Midpoint Assessment

1. Assessments, questionnaires, & other evaluations:
NEUROPSYCHOLOGICAL ASSESSMENTS: 1. BVMTR (Bender Visual Motor Gestalt Test -- evaluates visual-perceptual and visual-motor functioning, yielding possible signs of brain dysfunction, emotional problems, and developmental maturity) 2. Hopkins Verbal Learning Test (HVLT -- measure of verbal episodic memory) 3. Trailmaking Parts A and B (measure attention, visual searching, mental processing speed, and the ability to mentally control simultaneous stimulus patterns) 4. Digit-Symbol Substitution Task (measures brain damage, dementia, age and depression) 5. Grooved Pegboard dominant and non-dominant hand (Measures performance speed in a fine motor task. By examining both sides of the body, inferences may be drawn regarding possible lateral brain damage.) 6. Letter-Number Sequencing (tests working memory and attention) 7. Finger Tapping (measures motor speed) 8. FAS (measures executive cognitive dysfunction) 9. Action Fluency (examines verbally mediated executive functions, especially frontal system damage) 10. Stroop Interference Test (tests switching, cognitive flexibility and inhibition) 11. Digit Span (tests visuospatial and attention domains) 12. Rey-Osterrieth Complex Figure Test [Rey-O] (assesses visuospatial

abilities, memory, attention, planning, and working memory) 13. Wisconsin Cart Sorting Task [WCST -- computerized] (assesses executive functioning planning use of feedback and shifting) 14. Paced Auditory Serial Addition Task [PASAT] (assessment of speed of information processing) 15. Montreal Cognitive Assessment [MOCA] (screening assessment for mild cognitive impairment)

QUESTIONNAIRES: 16. Beck Depression Inventory (records symptoms of depression subjects have had in the past 2 weeks) 17. KMSK (Kreek-McHugh-Schluger-Kellogg scale -- designed to quantify self-exposure to opiates, cocaine, alcohol, tobacco and/or marijuana) 18. ADL questionnaire (questionnaire of ability to perform activities of daily living) 19. Substance Use Social Disruption Questionnaire (assessing social disruption from drugs and/or alcohol)

ACTIGRAPHY: Actigraph may be re-attached for approximately 1-2 weeks around the time of the midpoint assessment.

Stool sample and dietary survey.

E9

Re-screening Visit

1. Review of medical records (if not done previously)
2. Provision and documentation of written informed consent
3. UDS
4. Pregnancy test
5. HIV Dementia Scale (HDS)
6. CES-D depression scale
7. MRI questionnaire

E10

Follow-Up Visit(s) (can be performed same day as re-screening visit)

1. Neuromedical exam
2. History & physical
3. Vital signs (BP, HR, height, weight, waist circumference)
4. Assessments, questionnaires, & other evaluations:

NEUROPSYCHOLOGICAL ASSESSMENTS: 1. BVMTR (Bender Visual Motor Gestalt Test -- evaluates visual-perceptual and visual-motor functioning, yielding possible signs of brain dysfunction, emotional problems, and developmental maturity) 2. Hopkins Verbal Learning Test (HVLT -- measure of verbal episodic memory) 3. Trailmaking Parts A and B (measure attention, visual searching, mental processing speed, and the ability to mentally control simultaneous stimulus patterns) 4. Digit-Symbol Substitution Task (measures brain damage, dementia, age and depression) 5. Grooved Pegboard dominant and non-dominant hand (Measures performance speed in a fine motor task. By examining both sides of the body, inferences may be drawn regarding possible lateral brain damage.) 6. Letter-Number Sequencing (tests working memory and attention) 7. Wide Range Achievement Test (3 or 4) (Provides level of performance in reading, spelling, and written arithmetic. The reading and spelling tests are often used in estimating premorbid intellectual functioning.) 8. Timed Gait (standardized procedure assessing motor dysfunction of lower extremities and gait abnormalities associated with AIDS dementia complex) 9. Finger Tapping (measures motor speed) 10. FAS (measures executive cognitive dysfunction) 11. Category Fluency (animals) (tests executive functions and language, as well as semantic memory) 12. Action Fluency (examines verbally mediated executive functions, especially frontal system damage) 13. Stroop Interference Test (tests switching, cognitive flexibility and inhibition) 14. WAIS-III Symbol Search (tests perceptual organization and processing speed) 15. Iowa Gambling Task (computer exercise) (assessment of risk-taking) 16. Medication Management Task (listed as perf meas 1-5 on attachments) 17. Boston Naming Test (measures ability to retrieve words/language disturbance) 18. Digit Span (tests visuospatial and attention domains) 19. Line Orientation (tests visuospatial and attention domains) 20. Rey-Osterrieth Complex Figure Test [Rey-O] (assesses visuospatial abilities, memory, attention, planning, and working memory) 21. Wisconsin Cart Sorting Task [WCST -- computerized] (assesses executive functioning planning use of feedback and shifting) 22. Paced

Auditory Serial Addition Task [PASAT] (assessment of speed of information processing) 23. Montreal Cognitive Assessment [MOCA] (screening assessment for mild cognitive impairment) 24. Virtual Week (computerized prospective and retrospective memory assessment)

QUESTIONNAIRES: 25. Lawton & Brody ADL scale (assessment of ability to independently perform activities of daily living) 26. SES questions (looks at subjects' socioeconomic status, as well as previous early life trauma they may have experienced) 27. Risk Assessment Battery (assessment of risk-taking) 28. Beck Depression Inventory (records symptoms of depression subjects have had in the past 2 weeks) 29. KMSK (Kreek-McHugh-Schluger-Kellogg scale -- designed to quantify self-exposure to opiates, cocaine, alcohol, tobacco and/or marijuana) 30. Fagerstrom smoking questions (corrected version) (scale of nicotine dependence) 31. Locator Form (basic contact information, physicians' names, etc.; zip code will be used not only to contact participants, but also to determine median income for the area in which they live for data analyses) 32. Pittsburgh Sleep Quality Index (assesses sleep quality and disturbances over a 1-month interval) 33. ADL questionnaire (questionnaire of ability to perform activities of daily living) 34. Prospective and Retrospective Memory Questionnaire (PRMQ) 35. International Physical Activity Questionnaire (IPAQ) 36. Substance Use Social Disruption Questionnaire (assessing social disruption from drugs and/or alcohol)

ADDITIONAL ASSESSMENTS: 1. Fried Frailty Assessment 2. Calculation of the VACS index (captures both HIV and aging hallmarks to predict comorbidity and mortality) 3. Patient Centered Assessment and Counseling for Exercise (PACE) (assesses attitudes about exercise, barriers/facilitators to adherence to EXS, exercise enjoyment, self-efficacy and social support)

5. Cardiorespiratory capacity testing (including stationary bicycle (VO2 test), DXA and 6 minute walk test)
6. Attachment of actigraph at end of visit (if subject hasn't been wearing it throughout the intervention).
7. Removal of actigraph at last follow up appointment
8. Fasting labs (such as but not limited to CMP, sCRP, CBC w/diff, HbA1C, leptin, D-Dimer, YSI, Insulin/IFG-1/C-peptide/Glucagon, plasma BDNF, plasma VEGF, Adiponectin, IL-6, HOMA-IR/fasting glucose & insulin, glycosylated hemoglobin, plasma IGF-1, soluble CD163, plasma neopterin, galectin 9, etc.) and APOE test (APOE will only be done at baseline, not at follow up). CD4 and VL may also be collected if not available through medical records.
9. 3T MRI lasting approximately 1 hour
10. Stool sample and dietary survey.
11. Distribution of gym membership

If any of the testing procedures listed above have been completed recently (as determined by PI discretion) as part of another research study in which the subject has participated, data from those studies may be used as data for this study so as to not have the subject unnecessarily repeat procedures/create additional participant burden.

E11 Remote Visit:

Previously consented and enrolled participants will be contacted by phone to complete additional questionnaires regarding their experiences during the COVID-19 pandemic. Participants will have the option to complete the questions online through a RedCap generated survey or over the phone. The time to complete will vary, with an approximate duration of 1.5 hours. Questionnaires will be assessed approximately every 3 months for approximately 1-2 years.

Questionnaires:

- Florida COVID-19 Experiences
- Florida COVID-19 Stress
- HCP Symptoms and Medical Care Survey
- Florida COVID-19 Behaviors
- NIH Toolbox Emotion NIH TB Self-Efficacy CAT Age 18+

- Rotter's Locus of Control Scale
- International Physical Activity Questionnaire
- NIH Toolbox Emotion NIH TB Instrumental Support SF Age 18+
- Beck Depression Inventory
- Hospital Anxiety and Depression Scale (HADS)
- UCLA Loneliness Scale
- KMSK
- KMSK Social Disruption Scale
- Pittsburgh Sleep Quality Index
- NIH TB Perceived Stress CAT Age 18+
- HCP Financial Impact

E12 Safety and Adverse Events

All safety monitoring and reporting will be conducted in accordance with WU HRPO policies.

Data and Safety Monitoring Board

This protocol will include adverse event and other reporting by the PI and study coordinator to the Data and Safety Monitoring Board (DSMB). The conduct of this study will be reviewed annually by the DSMB. The DSMB will consist of: 1) [name] (Yale)- expert in neuroAIDS and HAND clinical trials; 2) [name] (UCSD)- expert in exercise physiology/neuroimaging; 3) [name] (WUSTL)- statistician with expertise in exercise clinical; 4) [name] (WUSTL)- an expert in aging and Alzheimer's disease clinical trials; and 5) program officer from NIH funding institute.

Serious adverse events will be reported to the IRB. The stopping criteria and guidelines to be used for this protocol will include the following: 1) The study will be stopped if there is clear evidence of harm or harmful side effects of the procedures used in this protocol; 2) In the event that a serious adverse event (SAE) occurs that increases the risks to participants, the study will be stopped and an investigation will be conducted and a findings report generated the PI and DSMB; 3) Should there be SAE or adverse event (AE) that occur at a frequency greater than 5%, it will be added to the consent document, if not already addressed and enrollment will be halted while a determination is made regarding the potential risks to participants. The risks of the intervention in this study population are low, however, the DSMB will review safety material.

Definitions and Reporting Guidelines and Timelines of Adverse Events

Same as defined by HRPO.

F Statistical Plan

Statistical Plan

Aim 1: Hypothesis 1a. Primary Analysis of the Study: We will assess if an EXS program in older sedentary PLWH enhances core NP domains (executive function, attention, and memory) compared to a SIS program. The change from baseline to 26 weeks after study intervention for each core domain Z- score and global Z-scores (comprised of the three core cognitive domain Z scores) will be compared between the EXS and SIS groups using t-tests. A 0.5 SD change in global Z-score is considered a clinically meaningful improvement and is currently being used for a pharmacotherapy (maraviroc) trial for HAND 149. In the present trial we anticipate that an EXS program will lead to >0.5 SD change in global Z-scores but we recognize that the precise threshold for individual perception of improvement is variable. For this analysis will use all random-ized subjects, under the intent-to-treat (ITT) paradigm. For participants missing a 26 week endpoint, a value will be imputed based on the lower (worse) half of the distribution from their arm (conservative approach).

Secondary analyses: Mean change in supplementary domain Z-scores at 26 weeks will be compared between the EXS and SIS groups for all randomized participants using the Z-test, under the following scenarios: (a) As treated (AT), with all subjects for whom the endpoint is available included in their allocated group; and (b) Per-protocol (PP), including only adherent participants ($\geq 80\%$ of study visits) for whom the 26 week endpoint is available. Additional multivariable secondary analyses will adjust for demographic and other relevant predictors, including plasma viral load and nadir CD4, gender,

depression, and other potential predictors that are significantly associated with the outcome at the 0.15 level using a backward model selection. In particular, the inclusion of gender and depression will allow for identification of differential changes in NP for men and women, and indirect effects of exercise mediated by depression 150-152. Since this is a medium-size randomized study we expect the unadjusted analysis to yield an unbiased estimate of the treatment effect. The outcomes will be collected only at baseline and follow-up, so a longitudinal analysis using generalized estimating equations or mixed effects models is not necessary as it would yield essentially identical results.

Principal Stratification (PS) Analysis: An additional exploratory secondary analysis will be done using a Principal Stratification framework 153. This analysis compares the treatment arms separately for four subsets determined by whether participants would adhere to the study on any of the two study arms or not. Accordingly, the four sets are: adherers on both EXS, SIS; non-adherers on both EXS, SIS; adherers on EXS but not on SIS; adherers on SIS but not on EXS. In practice these data are available for only one of the two statuses that the subject is randomized to, but the second status is effectively imputed statistically. This innovative analysis will allow for separate evaluation of effects of EXS intervention for those who can and those who cannot adhere to the exercise plan, and will give insights into the differential effectiveness of the EXS program.

Hypothesis 1b: We will assess if greater improvements in physical function due to an EXS program are associated with better cognitive performance. We will test the mediating effect of improvements in physical function on cognitive performance in two ways: (i) between randomized groups, and (ii) within the EXS group. Linear models will be used to determine the mediating effect of the physical function markers (high/low physical activity and peak VO₂) on the change from baseline in core domain specific Z-scores and the global Z-score, by including these markers, together with group assignment, as predictors in the model. Within the EXS group similar linear models will be fit (without the group variable). Similar analyses for supplemental Z-score domains will be explored in secondary analyses.

Exploratory analyses: A similar analysis will be conducted, (i) including both groups, and (ii) within the EXS group, evaluating the mediating effects of changes in glucose regulation (fasting glucose and HOMA-IR) and chronic inflammation (hsCRP, D-dimer, IL-6) on cognitive endpoints. Other variables to be assessed include neurogenesis factors (BDNF, IGF-1, and VEGF). Additional analyses will control for relevant predictors, using a backward model selection strategy as described above.

Aim 2. Hypothesis 2a. Primary Analysis of the Study: We will assess if an EXS program improves brain structure and function more than a SIS program in older sedentary PLWH. Changes in brain volumetrics (hippo-campus, caudate, and anterior cingulate) and regional CBF (hippocampus, caudate, and anterior cingulate) at baseline and 26 weeks will be compared between EXS and SIS groups using a similar design as for Aim 1, including ITT, AT, and PS analyses. The brain imaging outcomes will be adjusted for the relevant markers of brain size. A Holm-Bonferroni correction will be used when evaluating the brain volumetrics across the different regions 154.

Secondary analyses: Similar analyses will also be performed for brain volumetrics and regional CBF in the amygdala, thalamus, and putamen. Additional analyses will control for relevant predictors, using a backward model selection strategy, as mentioned above.

Hypothesis 2b: We will assess if greater improvements in physical function due to EXS are associated with larger brain volumetrics and increases in regional CBF. We will test the mediating effect of improvement of physical function on neuroimaging measures in two ways: (i) between randomized groups, and (ii) within the EXS group. Linear models will be used to determine the mediating effect of the physical function markers (high/low physical activity and peak VO₂) on the change from baseline in structural and functional neuroimaging measures, by including these markers, together with group assignment, as predictors in the model. Within the EXS group similar linear models will be fit (without the group variable).

Hypothesis 2c. We will assess if greater improvements in cognition are associated with improved brain structure and function changes. Linear models will examine the relationship between neurocognitive performance (outcome) and brain structural and functional changes (predictors), using only the 100 participants randomized to the EXS group. These models will adjust for potential confounders, (e.g. plasma viral load and nadir CD4) that are significantly associated with the outcome at the 0.15 level using backward model selection.

Exploratory analyses: A similar analysis will be conducted, (i) including both groups, and (ii) within the EXS group, evaluating the mediating effects of changes in glucose regulation (fasting glucose and HOMA-IR) and chronic inflammation (hsCRP, D-dimer, IL-6) on neuroimaging endpoints. Other variables that will also be assessed include neurogenesis factors (BDNF, IGF-1, and VEGF). Additional analyses will control

for relevant predictors, using a backward model selection strategy, as mentioned above.

Secondary endpoints: Scores from questionnaires that assess stage of behavior change, social support, self-efficacy, and exercise enjoyment will be incorporated with other quantitative outcome data. Logistic re-gression analyses will be conducted with response variables including: 1) successful complete (Y/N) 2) positive changes in cognitive function (Y/N); 3) positive change in brain structure and function (Y/N). The predictors will be the psychosocial or implementation factor scores. Odds ratios will be computed adjusting for demographic and other characteristics using backward model selection, as discussed before.

Additional Analyses: Baseline characteristics: Baseline demographic, medical, implementation factors, and lab characteristics of participants will be summarized by intervention arm (EXS or SIS) using N (%) for categorical variables, and mean, standard deviation, and range for numeric variables. Between-arms comparisons will use Fisher's exact test (FET) and Wilcoxon rank-sum test (WRST) for categorical and numeric variables, respectively. Neuroimaging comparisons will be adjusted via an analysis of covariance for measures of intra-cranial volume.

Study enrollment and drop-out: The number (%) of participants randomized, N (%) of participants completing 26 weeks, and N (%) of patients lost to follow-up will be summarized overall and by treatment arm, and compared between treatment arms using FET. For participants lost to follow-up we will record dates and reasons (if known) for loss to follow-up. Baseline demographic and medical characteristics will be compared between dropouts and completers using FET and WRST for categorical and numeric variables, respectively.

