Research team members conducting the focus groups will be trained specifically for that purpose, with particular emphasis on managing confidentiality and privacy both amongst group members and in respect to storing the data. All notes taken and recordings made during the group will be kept according to strict WUSTL HIPAA standards under the "2- lock" rule. Participants will be reminded that only the researchers will have access to their data, but that they also have a responsibility of keeping information discussed within the group confidential and not to converse about it outside of the group so that all members may feel safe in their self-expression. As an added measure of protection, group members will be asked to provide written informed consent and sign a confidentiality agreement to this effect before engaging in any group discussions. Since this study includes only PLWH, group participants will be notified of this before they commit to attending the group so they understand that while the study staff will never release their status, others participating in the group will know their status and may disclose this information to people outside of the group even though asked not to do so. For this reason, the names of group attendees will only be known to research staff and not to others attending the group, however, attendees that already know each other prior to enrolling in the study may still be at risk for having their status revealed.

2.f Early Withdrawal of Subjects

Participants will be reminded that they can withdraw their consent and drop out of the study at any point without being subject to retribution or any effects on their medical care. If subject chooses to drop out early or is withdrawn from the study, they will be invited to complete the follow-up evaluations (neuropsychological testing and questionnaires, MRI, cardiorespiratory capacity testing, fasting labs, neuromedical exam, actigraph measurement and stool sample) at that time. Should anyone's participation pose a risk after they have already begun the intervention, subjects will be evaluated on a case-by-case basis by the study team to determine if it is safe for them to continue in the study or should be withdrawn for their safety.

2.g Data Collection and Follow-up for Withdrawn Subjects

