Once a participant has been withdrawn from the study, either voluntarily or by study staff, no more data will be collected and follow-up will be provided as needed on a case-by-case basis. If a participant is withdrawn and then wants to get back in the study, s/he must be re-consented before any further study procedures are conducted.

D3 Study Intervention

3.a Description

After completing all screening assessments, subjects will be randomized in a 2:1 ratio (EXS:SIS) into one of the following 2 conditions:

EXS: All EXS sessions will be conducted at an indoor exercise facility at the WUSTL medical campus. Two sessions will be offered per weekday and will contain 10-12 participants. Each session will start with 5-10 min range of motion exercises. Participants will then follow his/her

individualized exercise training prescription based on baseline cardiovascular testing. Individual aerobic exercise intensity will be based on a percent of maximum heart rate (HRmax) achieved during the baseline cardiorespiratory fitness test (week -1). The target exercise HR will start at 50% and progress to 85% HR reserve (i.e., moderate to high intensity). During aerobic exercise, HR will be monitored by a battery-operated HR monitor (Polar, Lake Success, NY). HR and time spent exercising at target HR will be stored and documented daily to verify adherence and to calculate aerobic exercise energy expenditure. Exercise intensity (target HR) and duration (from 10 min up to 40 min) will be progressively increased as the participant acclimates to the exercise prescription. Adaptation will be determined when a given exercise intensity yields a lower HR than prior exercise sessions conducted at the same exercise intensity or the participant has a lower perceived exertion. The trainer will interact with each participant during their individualized exercise training and will provide feedback to ensure an appropriate rate of progression.

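### The primary analyses of both aims leave out the baseline value of the outcome; this costs precision, not validity, and the gain from adding it is modest

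*Combined protocol and SAP*

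**What the plan says.** Section F (Statistical Plan), Aim 1, Hypothesis 1a takes the change from baseline to 26 weeks in each core domain Z-score and in the global Z-score. These changes "will be compared between the EXS and SIS groups using t-tests". All randomised participants are included. For those without a 26-week endpoint, "a value will be imputed based on the lower (worse) half of the distribution from their arm".

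For Hypothesis 2a, the changes in regional volumes and blood flow "will be compared between EXS and SIS groups using a similar design as for Aim 1", with adjustment for markers of brain size. Under Additional Analyses the plan adds: "Neuroimaging comparisons will be adjusted via an analysis of covariance for measures of intra-cranial volume". That is an analysis of covariance, but not on the baseline value of the outcome.

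The adjusted models for Aim 1 are secondary. They name viral load, nadir CD4, gender and depression. The baseline score could enter only as one of the unnamed further predictors, if it passes backward selection at the 0.15 level. The plan defends its choice in two ways. First, "we expect the unadjusted analysis to yield an unbiased estimate of the treatment effect". Second, it sets mixed models and GEE aside on the ground that "The outcomes will be collected only at baseline and follow-up, so a longitudinal analysis using generalized estimating equations" and similar models would change almost nothing.

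**The concern.** A change score subtracts the whole baseline value. That is the most efficient use of baseline only in a special case. ANCOVA estimates the weight from the data, and with equal SDs at the two visits it is more precise for every r below 1. The plan's defence is that the estimate is unbiased. That is correct, but it does not address precision. The trial has 80% power for d = 0.49 only with all 150 outcomes, so precision that needs no new data is worth having.

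The sentence on visit timing raises a second, smaller question. E8 schedules a midpoint assessment with 15 of the 24 neuropsychological tests, and E7 puts the midpoint at about 3 months. Section F does not mention these scores.

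**Working it through.** **Inputs from the documents.** Allocation is 100 EXS and 50 SIS (E5). The power paragraph of section F states 80% power at d = 0.49 (150 randomised), 0.55 (80 + 40, the AT analyses after 20% drop-out) and 0.635 (60 + 30, per-protocol).

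**Assumptions.** Two-sided alpha of 0.05 (not stated); r from 0.6 to 0.95 (not stated); equal SDs at both visits unless noted; d in SDs of the change score unless noted.

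**Step 1: reproduce the plan.** Noncentral t power for an unadjusted t-test is 80.3% (100/50, d = 0.49), 80.4% (80/40, d = 0.55) and 80.2% (60/30, d = 0.635). The stated figures are right for the test chosen.

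**Step 2: variance ratio.** With unit SDs, the change score has variance 2(1−r) and the ANCOVA residual has variance 1−r². The ratio is (1−r²)/[2(1−r)] = (1+r)/2. At r = 0.7 this is 0.85, so ANCOVA with about 150 × 0.85 ≈ 128 participants matches the t-test with 150. Estimating the slope multiplies the variance by about 1 + 1/(N−4) = 1 + 1/146, or 0.7%, and uses one degree of freedom.

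**Step 3: power with 100/50 complete, d = 0.49, slope cost included.**

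| r | (1+r)/2 | Power, t-test | Power, ANCOVA | Detectable d (t-test 0.488) |
|---|---|---|---|---|
| 0.6 | 0.80 | 80% | 88% | 0.438 |
| 0.7 | 0.85 | 80% | 86% | 0.452 |
| 0.8 | 0.90 | 80% | 84% | 0.465 |
| 0.9 | 0.95 | 80% | 82% | 0.478 |
| 0.95 | 0.975 | 80% | 81% | 0.484 |

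**Step 4: unequal SDs.** With k = 26-week SD / baseline SD, the ratio is k²(1−r²)/(1+k²−2rk). At r = 0.7 it is 0.75 for k = 0.9 and 0.92 for k = 1.1.

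**Step 5: d in Z-score SDs.** The plan does not say which SD standardises d, and its target of more than 0.5 SD in the global Z-score may mean the Z-score SD. The change then has SD √[2(1−r)] = 0.894, 0.775, 0.632 at r = 0.6, 0.7, 0.8, and the ANCOVA residual has SD √(1−r²) = 0.800, 0.714, 0.600. With 100/50 and a difference of 0.49, t-test power is already 88%, 95% and 99%. ANCOVA raises it to 94%, 97.5% and 99.7%.

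**Step 6: the primary analysis as written.** It imputes missing values so that all 150 are analysed. I took the rule to be one random draw from the worse half of the arm's observed values, with 20% missing at random in each arm, no true effect and r = 0.6 to 0.8. Simulation then gives a variance ratio of about 0.86 to 0.93 if the change is imputed, and 0.87 to about 1.0 if the 26-week score is imputed. The drawn values are unrelated to the participant's own baseline (score imputed) or carry its full weight (change imputed), so the covariate explains less.

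**Step 7: AT analysis, 80/40, d = 0.49.** The t-test has 71% power. ANCOVA has 80%, 77% and 75% at r = 0.6, 0.7 and 0.8.

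**Step 8: midpoint scores.** With 20% random drop-out in each arm, using them lowers the variance by only 0.3% to 3.6% against ANCOVA in completers. With drop-out driven by decline but equal at 20% in each arm, the null bias of every method examined stays within 0.003 SD.

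**The case against.** The strongest case against is that the chosen test is valid, that the size of the gain depends on an r the documents do not give, and that changing two primary analyses at version 13, with the PI unblinded, is a high price for efficiency. The first two statements are true. They limit the claim to precision and require a range for r. For brain volumes r may be 0.9 or more, and the gain is then trivial.

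Three stronger readings are tempting, and the documents do not support them.

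- A reader might infer that the primary analysis has 71% power after drop-out and that ANCOVA would restore most of the loss. But the plan assigns the 80 + 40 figures to the AT analyses. The primary analysis imputes to 150, and step 6 applies there.
- A reader might infer that the sentence on visit timing is false. It speaks of the outcomes, which for Aim 1 are domain and global Z-scores. No section maps tests to domains. E8 omits Category Fluency, Line Orientation and Virtual Week, which E5 labels as tests of executive function, attention and memory. The payment table in I3 calls the midpoint battery a mini one, and E8 lists no MRI. The sentence may be true of the Z-scores.
- A reader might infer that rejecting longitudinal models is a serious error. After imputation the data are complete at two visits, and a mixed model with free arm means at baseline gives the same contrast as the change-score t-test. A model with a common baseline mean matches ANCOVA instead, so the remark is not general, but in its context it can be defended.

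**Conclusion.** The point holds as a loss of precision. The primary analyses of both aims omit a covariate that is already collected, and the secondary models do not name it. With complete data, 100/50 and d = 0.49 in change-score SDs, power would rise by 8 percentage points at r = 0.6 and by 1 point at r = 0.95. On the Z-score-SD reading the rise is about 6, 2.5 and 0.7 points at r = 0.6, 0.7 and 0.8. With the worse-half imputation kept, the variance saving is about 14% at most and may be nil. All of this rests on an assumed r, and steps 3, 5, 6 and 7 on equal SDs.

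There is no bias claim against the t-test under randomisation with complete data. On visit timing, the established point is narrow: section F does not mention a midpoint battery that repeats 15 of 24 tests, and whether the core domain scores can be formed then cannot be told.

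**What to change.** Blinded statistical staff should write the change and date it before the unblinding described in F1, because 2.d and 3.c leave the PI, the coordinator and the trainers unblinded.

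1. Make the primary analysis of both aims ANCOVA of the 26-week value on arm and baseline value. Keep the brain-size adjustment for Aim 2, and keep the change-score t-test as supportive.
2. State which SD standardises d, and state that the full gain is not reached while the worse-half imputation stays in the primary analysis.
3. Clarify the sentence on visits: say which tests form each domain Z-score, that 15 of the 24 tests are also given at midpoint, and how those scores will be used. Using them as auxiliary predictors for missing 26-week scores is optional and adds little.
4. Reconcile 2.f with 2.g. For participants who leave early, 2.f says "they will be invited to complete the follow-up evaluations (neuropsychological testing and questionnaires, MRI" and other listed assessments at that time. For withdrawn participants, 2.g says "no more data will be collected and follow-up will be provided as needed on a case-by-case basis". The statistical plan should then say how any such assessment enters the analysis.

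The cost is one degree of freedom, about 0.7% of variance, and a late amendment to two primary analyses. No new visits or data are needed.
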